6.2 Sample Size Considerations

Our primary comparison of interest is the effect on targeting of ACTs of offering a combination of outlet incentives for testing (provider-directed intervention), and ACT subsidies for malaria test-positive clients (client-directed intervention) relative to a control arm where outlets are able to offer malaria testing but neither the provider nor the client receives any extrinsic incentive to test (Arm 4 versus Arm 1). In order to evaluate whether the client-directed intervention and the provider-directed intervention do, in fact, have a synergistic effect on the outcome, we also have two secondary comparisons of interest: (1) the combined provider- and client-directed interventions relative to the provider-directed intervention alone (Arm 4 versus Arm 2) and (2) the combined provider- and client- directed interventions relative to the client-directed intervention alone (Arm 4 versus Arm 3).

We calculated power based on a cluster randomized two-sample two-tailed t-test for the comparison of two proportions using standard formulae [27]. We assumed 40 clusters (outlets) would be available to be enrolled based on information about the number of registered pharmacies in the study area. We calculated power for differences in our primary outcome for each of the three comparisons of interest noted above. To ensure that our overall two-tailed Type I error (alpha) is 5%, we fixed the alpha level at 1.667% (i.e. 5%/3) for each of the 3 comparisons of interest, using the conservative Bonferroni correction [28]. We estimated the intra-class correlation coefficients (ICCs) for the primary outcome to be 0.009 in Kenya.

Table 2: Assumptions in Kenya and Nigeria for sample size calculation for Aim 2

	Expected Percentage of ACTs taken by Clients Testing Positive for Malaria		Power (# of exit interviews per arm)		Our primary outcome—the proportion of ACTs that are taken by malaria test-positive clients—is a combination of the proportion of individuals who get tested for malaria and the proportion of tested individuals who treat
	Kenya	Nigeria	Kenya (1700)	Nigeria (2040)	
Arm 1: Control Arm (RDT only, no incentives)	12%	15%	>99%	>99%	
Arm 2: Provider-Directed Intervention (Shopkeeper incentives for malaria testing)	14%	17%	>99%	>99%	
Arm 3: Client-Directed Intervention (ACT subsidy to client conditional on positive test)	19%	26%	91%	89%	
Arm 4: Combined Provider- and Client-Directed Interventions	35%	40%	Ref. Group	Ref. Group	

according to the test result. We anticipate that 12% of ACTs will be purchased by clients with a positive test in the control arm (with 88% of ACTs purchased by those without a test or with a negative test). Moreover, we hypothesize that both the provider-directed intervention, and the client directed intervention on their own will only increase testing marginally (on the order of ~5 percentage points), but that among those who do test, the client-directed intervention alone will substantially increase the proportion of malaria-positive individuals who take an ACT [29]. As a result, we expect that the provider-directed intervention (Arm 2) will have only a small effect on ACT targeting, that the client-directed intervention (Arm 3) will have a somewhat larger effect, but that the largest effect will come from combining the two interventions (Arm 4) (i.e., we assume a statistical interaction). With a sample of 170 exit interviews per outlet (40 outlets in Kenya), we will have >90% power to detect a minimum difference between Arms 1 and 4 in the primary outcome of 23 percentage points. We will also have >89% power to detect a minimum difference of 16 percentage points for the main secondary comparison of interest (testing uptake).

Due to the nature of the interventions, it is not possible to blind participants and the implementation team to the allocation received. Data collectors will be blinded throughout collection and study statisticians will be blinded during the analysis phase.

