In order to align both the provider and customer incentives towards testing and targeting, the provider must be willing to perform the test and sell the appropriate medicine and, at the same time, the customer must be motivated to purchase the test and adhere to the results. We hypothesize that offering ACT subsidies for the client (conditional on a positive test), and incentives to the provider to offer malaria testing, will each, on their own, have a very modest impact on uptake of testing and targeting of ACTs in the retail sector. We further hypothesize that when combined, they will have a synergistic effect on RDT testing and ACT targeting. However, it is important to estimate the effect of each intervention separately and in combination in order to provide cogent evidence to support joint implementation. We will test the combination of subsidies for ACTs and RDTs (selected from Aim 1) paired with a provider-directed testing incentive in a four-arm cluster-

randomized controlled trial to evaluate their impact on the proportion of ACTs sold to individuals with parasitologically-confirmed malaria among those seeking care in the retail sector.

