3 STUDY DESIGN

This will be a four-arm cluster-randomized trial based on an underlying 2x2 factorial design. A random sample of 40 pharmacies (clusters) will be selected from a complete sampling frame of all eligible outlets and subsequently randomly assigned in a 1:1:1:1 ratio to each of the 4 arms (see Table 2).

All clusters (Arm 1-4) will have access to RDTs at the wholesale price that enables the outlet to charge the desired retail price. The study will pre-specify the retail price so that it is consistent across all the arms and pharmacies and will work with in-country wholesalers to provide RDTs at the appropriate price to all participating outlets. In addition, all outlets will be trained on a mobile reporting app and asked to use it to record RDT and ACT sales and to facilitate payment of financial incentives. The four treatment arms are as follows:

- (1) Control (Arm 1): No price subsidy or incentive. RDTs are made available at wholesale price to the retail outlet.
- (2) Provider-directed intervention (Arm 2): Retail outlet in this arm receives a small incentive to perform an RDT for suspected malaria cases (approximately USD \$0.10 for each RDT test they report)
- (3) Client-directed conditional ACT subsidy (Arm 3): Clients visiting outlets in this arm will receive a free ACT *if* they purchase a malaria test and have a positive test result.
- (4) Combined interventions (Arm 4): Retail outlets in this arm receive an incentive to test for malaria and clients visiting these outlets receive a free ACT conditional on a malaria positive test (i.e. this arm is a combination of the provider-directed and client-directed interventions that are offered in Arm 2 and Arm 3).

Our four-arm study design will allow us to measure the effect of joint incentives to the provider and consumer, relative to no incentives and relative to either incentive alone.

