In our previous work, we have had excellent retention of outlets in research activities and therefore have no reason to expect attrition of clusters. However, should one of the outlets selected choose to leave the study within the first 6 months of the intervention, the outlet will be replaced by one of the alternate outlets assigned to the same arm. If any outlet chooses to leave the study after the first 6 months of the intervention, they will not be replaced because, after joining the intervention at such a late stage, a newly added outlet is not likely to be comparable to that of all other participating outlets. Changes in the clusters (dropped and/or replaced) will be accounted for in the analysis.

Our sample size estimates correspond to a total of 6800 exit interviews with clients. Since not everyone interviewed will have purchased an ACT, our estimates account for the fact that only a subset will enter into our analysis for the primary outcome.

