6.4 Analysis Plan

We will analyze client-level outcomes by fitting a modified Poisson regression model [30, 31] with log link to estimate risk ratios (RRs) and identity link to estimate risk differences. Such an approach assumes a Poisson distribution for the binary outcome and then 'fixes' the estimated standard errors to correct for model misspecification.

To account for clustering by outlet we will use a generalized estimating equations (GEE) [32, 33] approach with exchangeable working covariance matrix and robust standard errors (to correct for model misspecification due to specifying a Poisson distribution). The outcome will be regressed on three binary indicators for each of the treatment arms 1-3, with treatment arm 4 (the combined interventions) serving as the reference group. The model will also include a vector of potential confounder variables (e.g., age, gender, education, household distance to closest health facility, study quarter) to account for possible imbalances between study arms. All analyses will be based on the intention-to-treat principle whereby all clients will be included in the analysis irrespective of whether they complied with the intervention in the outlet at which

they sought care (e.g. even if they did not use the ACT subsidy if they tested positive in an outlet in Arms 3 and 4 that received the client-directed intervention).

Given that the literature indicates that when there are fewer than 40 clusters in a cRCT, small sample correction methods should be used to ensure that standard error estimates are correctly estimated when using GEE to analyze binary outcomes, and given that the size of the cRCTs in each country are close to this cut-off, we plan to adopt the use of the Kauerman-Carroll correction to avoid any possible problems [34, 35]. We will compare secondary outcomes using the same modeling approach.

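### The two comparisons meant to evaluate synergy (Arm 4 vs 2, Arm 4 vs 3) test added benefit; the interaction itself has no specified test, scale, alpha or power

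*Combined protocol and SAP*

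**What the plan says.** - **Hypothesis (1.1).** Each intervention alone is expected to do little, and then: "We further hypothesize that when combined, they will have a synergistic effect on RDT testing and ACT targeting".
- **Design (3).** A 2x2 factorial structure with four arms, described as measuring joint incentives "relative to no incentives and relative to either incentive alone".
- **Comparisons (6.2).** The primary comparison is Arm 4 versus Arm 1. To find out whether the two interventions "do, in fact, have a synergistic effect on the outcome, we also have two secondary comparisons of interest", the plan adds Arm 4 versus Arm 2 and Arm 4 versus Arm 3. The 5% alpha is split over these three comparisons (1.667% each), and power is given only for them.
- **Sizing (6.2).** The expected percentages of ACTs taken by test-positive clients are 12, 14, 19 and 35% in Arms 1 to 4, explained by the remark "i.e., we assume a statistical interaction".
- **Denominator (6.3).** Of the interviews, "only a subset will enter into our analysis for the primary outcome". The size of that subset is not given.
- **Model (6.4).** "The outcome will be regressed on three binary indicators for each of the treatment arms 1-3", with Arm 4 as reference. It is fitted with a log link for risk ratios and an identity link for risk differences. No interaction contrast is named.

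**The concern.** Synergy here means that the combination does more than the separate effects predict. That is how 1.1 sets it against modest single effects, and 6.2 itself calls it a statistical interaction. Judging it requires all four arms. The two comparisons given that task each leave out Arm 1, so they show that the combination beats each component, not that it beats their sum or product.

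Two consequences follow. First, purely additive effects could be reported as synergy. Second, if an interaction is computed later, its scale, alpha and standing would be chosen after the data are seen. Interaction depends on the scale, and the plan estimates both risk ratios and risk differences. The plan sets no rule that two significant results establish synergy, so the danger is misreading rather than a built-in false claim.

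**Working it through.** **1. What the comparisons estimate.** Write p1 to p4 for the arm proportions. Let the provider effect be a = p2 − p1, the client effect c = p3 − p1, and the interaction I = p4 − p3 − p2 + p1. Then

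- Arm 4 − Arm 2 = c + I
- Arm 4 − Arm 3 = a + I

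Both can be positive with I = 0, or with I < 0 if a and c are large enough.

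**2. The interaction implied by the plan's rates (6.2, Table 2).**

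- Additive value for Arm 4: 14 + 19 − 12 = 21%. Interaction: 35 − 21 = 14 points.
- Multiplicative value: 14 × 19 / 12 = 22.2%. Ratio of risk ratios: (35 × 12)/(14 × 19) = 1.58.

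**3. Reproducing the stated power.** Inputs: ICC 0.009, 10 outlets per arm (40 outlets, 1:1:1:1), alpha 1.667% two-sided, and m ACT buyers per outlet. The variance of an arm proportion is p(1−p)[1 + (m−1)0.009]/(10m).

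- With m = 170 (every interview counted), 35% versus 19% has power above 99.9%, not 91%. Section 6.3 says that only a subset counts, so this is no contradiction, but m must be inferred.
- Solving for 91% gives m = 25.3 (normal) or 31.4 (t, 18 df). For example, at m = 25.3 the standard error is 0.0429, 0.16/0.0429 = 3.73, and 3.73 − 2.39 = 1.34, which gives 91%. With the same method at the same m, Arm 4 versus 1 and Arm 4 versus 2 exceed 99%, in line with Table 2.

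I therefore use m = 25–31 as an assumption and 170 as the upper bound.

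**4. Power for the interaction at the plan's rates.** The variance of the difference contrast is the sum of the four arm variances, with Σp(1−p) = 0.6074. For the log ratio of risk ratios (delta method), p(1−p) is replaced by (1−p)/p, with sum 19.60. At m = 25 the standard errors are 0.0544 (against 0.14) and 0.309 (against ln 1.58 = 0.457). Ranges run from t with 36 df to normal.

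| m | Difference, 5% | Difference, 1.667% | Ratio, 5% | Ratio, 1.667% |
|---|---|---|---|---|
| 25 | 71–73% | 53–57% | 30–32% | 17–18% |
| 31.4 | 78–81% | 62–67% | 35–37% | 20–22% |
| 50 | 90–92% | 79–83% | 46–49% | 29–32% |
| 170 | >99% | 98–99% | 74–76% | 57–61% |

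**5. How often both comparisons are significant at 1.667% without synergy.** Beta-binomial simulation, 40,000 trials per cell. Ranges run from a cluster-level t test to a normal test with known ICC.

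| Arms 1/2/3/4 (%) | True I (points) | m = 25 | m = 31 | m = 170 |
|---|---|---|---|---|
| 12/14/19/21 (plan's single-arm effects, additive) | 0 | 2.0–2.4% | 2.1–2.6% | 6.1–7.0% |
| 12/23.5/23.5/35 (assumed, additive) | 0 | 33–42% | 41–51% | 94–98% |
| 12/25/25/35 (assumed, sub-additive) | −3 | 21–27% | 28–35% | 84–91% |

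In the two additive cases the difference-scale interaction test rejects at 4.9–5.2%, as it should at 5%. The second row also shows why the scale matters: its multiplicative value for Arm 4 is 23.5 × 23.5 / 12 = 46.0%, so the same data are additive as differences and antagonistic as ratios.

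**The case against.** The best reply is that little is at stake under the plan's own expectations. If the single interventions give only 14% and 19%, and effects simply add, both comparisons come out significant in only 2–3% of trials at 25–31 buyers and 6–7% at 170. The larger figures come from assumed rates with much stronger single effects. Intermediate additive cases, by cluster-level t test, give about 4–5% (12/17/17/22%) and 9–12% (12/19/19/26%) at 25–31 buyers, rising to 24% and 52% at 170. This stands, and it limits the weight of the point. It relies, however, on the single-arm effects that the trial is meant to estimate.

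Second, the decision question is answered: whether the combination beats nothing and beats either incentive alone. That also stands. The comparisons are sound and should stay; only the purpose attached to them is wrong.

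Third, the interaction is a linear combination of coefficients that the model already yields. True, and it makes the remedy cheap, but it does not fix scale, alpha or status in advance.

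Fourth, the plan states no interaction power, which is not the same as inadequate power. Agreed: on the difference scale at 5% it is 90–92% at 50 buyers and above 99% at 170.

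**Conclusion.** The concern holds and should be fixed. The analysis specified in 6.2 and 6.4 does not answer the synergy question posed in 1.1 and 6.2. Arm 4 versus 1, and the two added-benefit comparisons taken as such, are unaffected.

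The risk of misreading runs from about 2–3% under the plan's single-arm effects to 33–51% under stronger additive effects, both at 25–31 buyers per outlet, and to 94–98% for the latter at 170. Power for the real question at 5% is about 71–81% (differences) or 30–37% (ratios) at 25–31 buyers, against the 91% stated for Arm 4 versus 3.

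These figures assume ICC 0.009, ten outlets per arm, equal numbers of ACT buyers in every arm, and no covariate adjustment. The buyer count is inferred from the 91%, not documented. No interaction power can be computed for testing uptake, because arm-level testing rates are not given.

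**What to change.** Either of two routes removes the mismatch.

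**Test it.** In 6.2 and 6.4, pre-specify the interaction contrast for the primary outcome and for testing uptake.
- Name one scale that decides the synergy claim, for example the risk-difference contrast Arm 4 − Arm 3 − Arm 2 + Arm 1. With Arm 4 as reference in the identity-link fit, this is b1 − b2 − b3.
- Report the ratio of risk ratios from the log-link fit as supportive, and give each with a confidence interval.
- State the alpha and whether the contrast belongs to the Bonferroni family.
- Relabel Arm 4 versus 2 and Arm 4 versus 3 as tests of added benefit.
- Give interaction power by scale, as a range over the assumed ACT buyers per outlet.

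**Or do not claim it.** Remove the synergy purpose from 6.2 and say that the hypothesis in 1.1 will not be formally tested.

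The first route costs wording and one linear contrast, with no new outlets, interviews or data. If the contrast joins the family as a fourth test (5%/4 = 1.25%), Arm 4 versus 3 falls from 91% to about 89%, and difference-scale interaction power at 25–31 buyers is about 49–63%. Adding the testing outcome to that family would cost more. Outside the family, the three existing comparisons lose nothing. The second route has no alpha cost.

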2.16	Did the client show documentation of the prescription?	
1. No
 
2. Yes, a written prescription from the provider/facility/lab
 
3. Yes, other (Specify: _____)
	

Section 3: Test at Shop

Number	QUESTION	RESPONSE	SKIP
3.1	Did you (or your child) have your blood tested for malaria today at the shop?	
1. Yes
 
2. No
	If yes skip to 3.3
3.2	Why not? (Mark all that apply)	
1. Too expensive
 
2. RDT was not offered
 
3. RDT not in stock
 
4. No time
 
5. Already sure illness is malaria
 
6. Already sure illness is not malaria
 
7. Don't want to get finger pricked
 
8. Was tested elsewhere before coming
 
9. Had a prescription for drug I needed before coming
 
99. Other Specify: _____
	Next skip to section 4
3.3	RDT results from shop (self-report)	
1. Negative
 
2. Positive
 
3. Invalid
	
3.4	How likely is it that the result of the test was correct? Only if tested	
1. Not possible
 
2. Unlikely but not impossible
 
3. 50/50
 
4. Likely
	

		5. Absolutely sure Don't know	
--	--	----------------------------------	--

Section 4: Purchase Questions

Number	QUESTION	RESPONSE	SKIP
4.1	Which medicine(s) did you obtain from the shop today to treat your/your child's illness Choose all that apply,	
 1. AL (Lonart/CoArtem/Artefan) 2. Other ACT (DHAP, DP, Duocotexin, P-alaxin) 3. Other antimalarial (Artesunate injection, Quinine, Chloroquine, SP/Fansidar) 4. Antibiotic (Amoxyl/Ceptrin, Metronidazole/Flagyl/Ampicillin) 5. Painkiller/fever medicine (Panadol/Brufen/Hedex/ Action/Maramoja) 6. Cough medicine or decongestant 7. Other _____ 8. None 
99. Don't know
	If 2, 3, 4, 5, 6, 7 or 99 Skip to 4.4 If 8, skip to 5.1
4.2	How much did you pay today for the ACT? (The amount refers to how much money respondent paid for the ACT. Don't add the amount of the voucher if any was used-the amount should be between 0-5000, or 9999 for don't know)	ACT= _____ KES OR Don't know/remember...9999	
4.3	How much did you spend at the pharmacy today? (Total cost to client including RDT, ACT and any other drugs)	_____ KES	
4.4	Was there any discount for your ACT at the shop today?	
 1. Yes 2. No 3. Don't know 	

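### Data collectors are said to be blinded throughout, but their own exit interview can show them which outlets have the client subsidy (Arms 3/4 against Arms 1/2)

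*Combined protocol and SAP*

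**What the plan says.** Section 6.2 concedes that "it is not possible to blind participants and the implementation team to the allocation received". It then says: "Data collectors will be blinded throughout collection". The same sentence has the statisticians blinded for the analysis. No step that would keep collectors blinded is described.

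Section 3 defines the arms. In Arm 3, "Clients visiting outlets in this arm will receive a free ACT" if they buy a test and it is positive. In Arm 4, "clients visiting these outlets receive a free ACT conditional on a malaria positive test", and the outlet is also paid to test. Arm 1 has "No price subsidy or incentive". Arm 2 has only the payment to the outlet.

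The collectors' form is in Appendix A.1. Its items run in this order: tested at the shop (3.1), shop result by self-report (3.3), medicines obtained (4.1), amount paid for the ACT with 0 KES allowed (4.2), ACT discount (4.4), and type, brand and price of each drug (4.5). Item 4.4 asks "Was there any discount for your ACT at the shop today". Item 4.2 carries a note telling the interviewer not to add "the amount of the voucher if any was used".

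Under section 8 the interviewer also screens and obtains consent. Section 3 sets a target of 10 participants per outlet per month and assigns collectors to outlets at random. The stated reason for the random assignment is to limit behaviour change caused by the interviewer's presence.

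**The concern.** The blinding statement covers the whole collection period, yet the instrument asks about the feature that separates two arms from the other two. Once one client reports a positive shop test and an ACT at no cost, the collector knows that the outlet has the client subsidy. The same person may then screen, obtain consent from and interview further clients there.

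Two things are at stake. The trial could not accurately report that outcome assessment was blinded. Recruitment or recording after the reveal could also differ by arm. The primary comparison (Arm 4 v 1) and one secondary comparison (Arm 4 v 2) both cross the revealed split. The plan chose exit interviews to avoid bias in provider-reported data, so the collector's independence carries weight in this design.

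**Working it through.** **1. Is there a contradiction?**

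- Arms 3 and 4: a purchased shop test with a positive result leads to a free ACT (section 3).
- Arms 1 and 2: no client subsidy (section 3).
- Form: the shop result (3.3) and a zero ACT price (4.2 or 4.5) are recorded in the same interview.

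A positive shop test followed by a zero price therefore identifies Arms 3/4. No exit item asks about the provider payment, so the form separates neither Arm 3 from Arm 4 nor Arm 1 from Arm 2. The outcome items (3.1, 3.3, 4.1) precede the price items, so the revealing interview is itself largely protected. What comes after it is not.

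**2. ACT buyers per outlet implied by the plan's power figure.** The plan does not give this number. Section 6.3 says only that a subset of interviewees enters the primary analysis.

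Inputs from section 6.2: 19% (Arm 3) v 35% (Arm 4), ICC 0.009, alpha 5%/3 = 1.667%, stated power 91%. There are 10 outlets per arm (40/4). With m buyers per outlet:

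- Design effect = 1 + (m − 1) × 0.009
- SE = √[(0.19 × 0.81 + 0.35 × 0.65) × design effect / (10m)]
- Noncentrality = 0.16 / SE

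| m | Design effect | Noncentrality | Power, normal | Power, t with 18 df |
|---|---|---|---|---|
| 25 | 1.216 | 3.715 | 90.7% | 84.6% |
| 28 | 1.243 | 3.888 | 93.3% | 88.1% |
| 31 | 1.270 | 4.048 | 95.1% | 90.7% |
| 170 | 2.521 | 6.728 | >99.9% | >99.9% |

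The stated 91% corresponds to about 25 buyers (normal) or 31 (t). I take the midpoint, 28, which is 28/170 = 16.5% of interviews.

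**3. Chance of at least one reveal at an outlet.** Let q = 28 × (share of ACTs going to test-positive clients) × e / 170, where e is the fraction of those positives who were tested at the outlet. Only they qualify for the subsidy (section 3). The documents do not give e, so I show 1.0 (the upper bound) and 0.5 (an assumption). The chance over n interviews is 1 − (1 − q)^n, treating interviews as independent.

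| Arm | e | Expected reveals in 170 | q | n = 10 | n = 170 |
|---|---|---|---|---|---|
| 4 | 1.0 | 28 × 0.35 = 9.8 | 5.8% | 45% | >99.9% |
| 3 | 1.0 | 28 × 0.19 = 5.3 | 3.1% | 27% | 99.5% |
| 4 | 0.5 | 4.9 | 2.9% | 25% | 99% |
| 3 | 0.5 | 2.7 | 1.6% | 15% | 93% |

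**4. Sensitivity to the number of buyers.** With 25 buyers and e = 0.5, the figures are 23% (Arm 4) and 13% (Arm 3) for 10 interviews, and 99% and 91% for 170. If instead 30% to 80% of interviewees buy an ACT (an assumption) and e lies between 0.5 and 1, the figures for 10 interviews are 42% to 96% (Arm 4) and 25% to 81% (Arm 3). Those for 170 are at least 99% in both.

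**The case against.** The strongest opposing case is that the unblinding is partial, its reach is uncertain, and the route to bias is narrow.

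- **Partial.** Only the client-subsidy factor shows. A reader might infer that blinding fails completely. The documents do not support that: the provider incentive stays hidden and Arm 4 v 3 does not cross the revealed split. This stands.
- **Voucher and discount wording.** A reader might infer that the form asks about vouchers. It does not; the word occurs only in an interviewer note in item 4.2. A yes to item 4.4 alone could be the outlet's own discount. The strong signal is a zero price after a positive shop test. This stands.
- **Same collector, same outlet.** A reader might infer that one collector returns and keeps interviewing with this knowledge. The documents do not say so, and assignment is random. The figures above describe outlets, not what any one person knows. This stands, but nothing in the plan limits return visits or sharing among collectors, and later interviews on the same day are exposed in any case.
- **Little room for judgement.** Suspecting malaria is the client's own view, fever is a reported fact, and the outcome items are closed. Only severe illness rests much on the collector. The plan also photographs every RDT and compares exit with provider data by outlet. This largely stands for recording. It does not address who is approached or enrolled.

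None of this rescues the statement that collectors stay blinded throughout.

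**Conclusion.** The sentence in section 6.2 claims a property that the design does not have for the client-subsidy factor. That follows from the arm definitions and the form alone.

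The size rests on assumptions: 28 ACT buyers per outlet inferred from the stated power, independent interviews, and an unknown share of positives tested elsewhere. On those terms, a reveal at an outlet within 10 interviews (one month's target) has a chance of at most about 45% in Arm 4 and 27% in Arm 3. Over all 170 interviews it is above 90% in both arms, even with half of the positives documented elsewhere. A larger share of ACT buyers would raise the monthly figures.

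A reader might go further and conclude that the results will be biased. The documents show neither that nor a direction. The figures count reveals, not bias. The point concerns an inaccurate design statement and missing by-arm reporting. It is not evidence against the planned comparisons.

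**What to change.** 1. Replace the statement on data collectors in section 6.2 with wording such as: *data collectors are not told the allocation, but client-subsidy status (Arms 3/4) is expected to become apparent from price and discount answers.* The statement about the statisticians can stay.
2. Report by arm the numbers screened, excluded by reason, refused and consented, from items 0.01 to 0.03. This is the check on selective recruitment.
3. Break the comparison of exit interviews with provider reports, already planned in section 3, down by arm. It covers proportion tested, test positivity and ACT use by test status, so it can serve as the check on differential recording.

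A sensitivity analysis limited to purchases where the drug was shown (item 4.5) is not recommended. It would verify the drug but not the self-reported test result, and it does nothing about recruitment.

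The cost is a less favourable blinding statement and a small amount of extra reporting. The screening items exist and no price item need be dropped.
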